### 4.2 Inclusion criteria

In order to be eligible to participate in this study, a subject must meet all of the following criteria:

1. Age 18 years or older;
2. Probable diagnosis of acute stroke, as assessed by the paramedic in the prehospital setting;
3. Score of 2 or 3 on the Face Arm Speech Test (FAST, Appendix 3);
4. Systolic blood pressure  $\geq$  140 mm Hg;
5. Possibility to start the trial treatment within 3 hours of symptom onset;
6. Intention to transport the patient to one of the participating hospitals;
7. Written informed consent (deferred).

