## **8.4 Withdrawal of individual subjects**

Subjects can leave the study at any time for any reason if they wish to do so without any consequences. The investigator can decide to withdraw a subject from the study for urgent medical reasons. The reason for withdrawal, if available, will be recorded in the eCRF. Data from non-consenting subjects will only be used when there is no written objection from the subject or representative. In an effort to describe the non-consenting population we will ask the subject or his/her representative to allow the use of routinely collected data in a coded manner. If no consent for the use of these data is obtained, only the following will be noted: study number, treatment allocation and refusal.

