### **8.5 Replacement of individual subjects after withdrawal**

For each patient that withdraws before the final outcome assessment, an additional patient will be included.

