### **8.6 Follow-up of subjects withdrawn from treatment**

In patients who discontinue their allocated treatment, this event will be recorded, including the reason for discontinuation if available. Further treatment will be at the discretion of the treating physician. Follow-up will be carried out as planned.

Due to the deferred consent procedure, study medication has been administered to patients randomised to GTN before informed consent has been obtained. Therefore it is not ethical, for the safety of all patients in the study, to eliminate all information of patients who do not provide informed consent in case of a serious adverse event in the first 7 days, or death during the full study period (both important safety variables for the study). Eliminating these records could result in an underestimation of the true risk of the study treatment and reduce the validity of the data and could lead to major safety concerns for all patients in case patients with a poor outcome will selectively withdraw from study participation. To overcome this safety concern, we will register for non-consenting patients only the variables: patient's study number, date of randomisation, study treatment, final diagnosis, investigator reported serious adverse events in the first 7 days (or until hospital discharge, if earlier), in-hospital mortality (yes/no). All other information will completely be erased from the patient's study record. The link to the study database will be erased from the medical record.

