## 10. STATISTICAL ANALYSIS

### 10.1 Statistical analysis plan (SAP)

The analysis and reporting of the trial will be in accordance with CONSORT guidelines. Before follow-up will have been completed, a statistical analysis plan (SAP) will be developed that will specify: (i) Hypotheses to be tested; (ii) Treatment effects to be estimated in order to satisfy the primary and secondary objectives of this trial; (iii) Technical description of the statistical methodology and procedures for performing the statistical analysis of outcome measures and SAE data; (iv) Primary, secondary, and sensitivity analyses; and (v) Subgroup analyses. The SAP will be signed off by the trial Executive Committee and then uploaded on the public area of the trial website. The final statistical analysis will be performed once recruitment has ceased, final follow-up has been completed, final data have been checked and any errors corrected, and the database has been locked.

All analyses will be performed according to the intention-to-treat principle. Baseline data by treatment allocation will be reported with statistical procedures. Missing values for baseline characteristics will be reported. Missing baseline characteristics will be imputed using regression imputation.

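### Sections 8.4, 8.6 and 11.2 give incompatible rules on what is kept for patients who refuse deferred consent, so early SAEs and deaths can be lost from the safety comparison

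*Protocol*

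**What the plan says.** Consent is sought after enrolment and after treatment has started (Section 11.2). Patients and treating staff know the allocation (Section 8.2). Three sets of text then govern the data of a patient who refuses.

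- **Section 8.4** asks refusers to allow coded use of routinely collected data. Failing that: "If no consent for the use of these data is obtained, only the following will be noted: study number, treatment allocation and refusal".
- **Section 8.6** has its own list: "we will register for non-consenting patients only the variables: patient's study number, date of randomisation, study treatment, final diagnosis, investigator reported serious adverse events". The SAEs meant are those up to day 7, or up to discharge where that comes sooner. The list closes, and the rest is dropped, as follows: "in-hospital mortality (yes/no). All other information will completely be erased from the patient's study record". Under the same section, the medical record loses its connection with the trial database.
- **Sections 8.4 and 11.2** both say that a non-consenting patient's data are used only if nobody has objected in writing. Section 8.6 does not mention a written objection.

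Section 8.6 gives its reason. It names two variables that matter for safety, SAEs in the first 7 days and death at any time in the study, and calls it unethical to eliminate this information.

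**The concern.** Sections 8.4 and 8.6 each give a closed list for patients who withhold consent, and the lists differ. A site following 8.4 records no SAE, death or diagnosis for a patient who refuses both participation and data use. A site following 8.6 records all three. Neither section refers to the other.

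This matters because refusal comes after randomisation. By then the allocation is known, and often the early clinical course as well, so willingness to consent may depend on both. Section 8.6 recognises this: "Eliminating these records could result in an underestimation of the true risk of the study treatment". Sections 1.10 and 13.2 say that the tendency towards harm in subgroups of the earlier ambulance-based trial calls for close safety monitoring. An ambiguous retention rule weakens that monitoring, and an analysis plan cannot recover events that were never kept.

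**Working it through.** The protocol has no figure to reproduce on this point. It gives no expected refusal rate, and the step from 1280 to 1400 patients in Section 4.4 is for stroke mimics only. The check is therefore mainly a comparison of the texts.

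**Step 1: the two lists**

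| Item | 8.4, data use also refused | 8.6, non-consenting |
|---|---|---|
| Study number | kept | kept |
| Allocation / study treatment | kept | kept |
| Fact of refusal | kept | not listed |
| Randomisation date | not kept | kept |
| Final diagnosis | not kept | kept |
| SAEs to day 7 or discharge | not kept | kept |
| In-hospital death | not kept | kept |
| Death after discharge | not kept | not kept |

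**Step 2: which rule applies to whom**

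- *Refuses participation, allows routine data.* Section 8.4 lets the routine data be used. Section 8.6 erases everything outside its list.
- *Refuses both, no written objection.* Section 8.4 keeps three items and no safety data. Section 8.6 keeps the safety data.
- *Objects in writing.* Sections 8.4 and 11.2 bar use. Section 8.6 has no exception and would still register its list.
- *Dies before consent is asked.* Section 11.2 provides for informing the representative, and the deferred-consent appendix allows the data documented so far to be used. The rules do not conflict here.

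The instructions differ in the first three situations. In the second and third, the difference is whether SAEs and deaths are available for analysis.

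**Step 3: Section 8.6 against its own aim**

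The aim covers death throughout the study, with final follow-up at 90 days. The retained variable is in-hospital death, yes or no. A refuser who dies after discharge and before day 90 is therefore lost even if 8.6 is followed exactly.

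**Step 4: illustration of what 8.4 could do (assumed inputs)**

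- 700 GTN patients = 1400/2. Equal allocation is assumed; the protocol does not state it.
- True SAE risk t = 14% in both arms. Section 13.1(e) gives 14% and 13% for the arms of the earlier phase III trial; this is not the present trial's own 7-day rate.
- A share x of GTN patients with an SAE is lost through refusal, and nobody else is. This is an assumption, shown over a range.

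GTN patients with an SAE: 700 × 0.14 = 98. Visible rate = t(1 − x) / [t(1 − x) + (1 − t)].

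| x | Patients with an SAE lost | Visible GTN rate | Apparent difference from 14% |
|---|---|---|---|
| 5% | 98 × 0.05 = 4.9 | 0.133/0.993 = 13.4% | 0.6 points |
| 10% | 98 × 0.10 = 9.8 | 0.126/0.986 = 12.8% | 1.2 points |
| 20% | 98 × 0.20 = 19.6 | 0.112/0.972 = 11.5% | 2.5 points |

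If the loss fell on controls instead, the sign would reverse. If it were equal in both arms, both rates would be understated and the difference would be nil. Under 8.6 none of these early SAEs would be lost.

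**The case against.** **Section 8.6 may be a safety exception to 8.4.** This is the natural way to reconcile them, and it is why 8.6 is the better base for a single rule. But no text says so, and 8.6 is headed as follow-up of patients withdrawn from treatment, so a site handling a refusal could reasonably stop at 8.4.

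**Few patients may be affected.** The restrictive sentence in 8.4 reaches only those who refuse twice, and deaths before consent are handled separately. Both points stand. They limit the number by an unknown amount.

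**SAEs may already have been reported.** Section 9.2.2 requires most SAEs up to day 7 to reach the sponsor within 24 hours, with no consent exception, and Section 9.5 gives the DSMB listings of all SAE reports. Events reported before refusal may therefore be on file, and it would be too strong to say that refusers' events vanish from DSMB review. However, expected SAEs are exempt from expedited reporting and go into the eCRF within 7 days. Appendix 9 counts haematoma expansion and arterial hypotension among them. Nothing in 8.4 says that events already entered are kept for analysis.

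**Stronger readings that the protocol does not support**

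- *A reader might infer that intention-to-treat is not achieved.* Section 10.1 says "All analyses will be performed according to the intention-to-treat principle" and leaves methods and sensitivity analyses to an SAP that is not available here. Some loss of 90-day outcomes is inherent in deferred consent, and analysis sets and missing mRS scores may be dealt with in that plan.
- *A reader might infer that replacement breaks the randomised comparison.* Section 8.5 says "For each patient that withdraws before the final outcome assessment, an additional patient will be included". This adds a patient; it does not remove the withdrawn one from the flow or the denominators.
- *A reader might infer from inclusion item 7, "Written informed consent (deferred", that early deaths are ineligible.* The item itself says that consent is deferred, and Section 11.2 and the deferred-consent appendix provide for death before consent.

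**Conclusion.** Two textual defects are established. The retention rules in 8.4, 8.6 and 11.2 cannot all be followed, and the mortality variable in 8.6 falls short of the aim stated in the same section. Because refusal follows open-label allocation and treatment, following 8.4 can remove SAEs and deaths selectively by arm, which is the harm that 8.6 sets out to prevent.

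Size and direction are unknown. The protocol gives neither a refusal rate nor the share of refusers who also decline data use, so the tabulated shifts of 0.6 to 2.5 points show only what the assumed selective losses would do. The verdict rests on the wording and on the possibility of selective refusal, not on evidence that it occurs. It concerns the safety comparison and does not extend to a failure of the primary analysis.

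**What to change.** With the agreement of the ethics committee:

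1. Make the minimum safety data set in 8.6 the single rule for refusers, and delete the conflicting last sentence of 8.4. Add the fact of refusal, which 8.6 does not list.
2. State in 8.4 and 11.2 what a written objection does to that data set, and refer to the statement from 8.6. Deleting the sentence in 8.4 does not settle this.
3. Say whether the erasure in 8.6 applies to refusers who allow coded use of routine data.
4. Align mortality in 8.6 with its aim: either keep vital status to day 90 where permitted, or restate the aim as in-hospital death.
5. Analyse 7-day SAEs and the retained mortality variable in all randomised patients, refusers included, and report refusals by arm.

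Two optional clarifications: state that replaced patients stay in the flow and denominators, and that patients who die before consent stay in the analysis.

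The cost is protocol wording and agreement with the ethics committee. No new measurement is needed, except that keeping vital status to day 90 would require permission and a link that is retained until then.

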### **8.5 Replacement of individual subjects after withdrawal**

For each patient that withdraws before the final outcome assessment, an additional patient will be included.

### **8.6 Follow-up of subjects withdrawn from treatment**

In patients who discontinue their allocated treatment, this event will be recorded, including the reason for discontinuation if available. Further treatment will be at the discretion of the treating physician. Follow-up will be carried out as planned.

Due to the deferred consent procedure, study medication has been administered to patients randomised to GTN before informed consent has been obtained. Therefore it is not ethical, for the safety of all patients in the study, to eliminate all information of patients who do not provide informed consent in case of a serious adverse event in the first 7 days, or death during the full study period (both important safety variables for the study). Eliminating these records could result in an underestimation of the true risk of the study treatment and reduce the validity of the data and could lead to major safety concerns for all patients in case patients with a poor outcome will selectively withdraw from study participation. To overcome this safety concern, we will register for non-consenting patients only the variables: patient's study number, date of randomisation, study treatment, final diagnosis, investigator reported serious adverse events in the first 7 days (or until hospital discharge, if earlier), in-hospital mortality (yes/no). All other information will completely be erased from the patient's study record. The link to the study database will be erased from the medical record.

### **8.7 Premature termination of the study**

If the Sponsor, the Investigator(s), or Regulatory Authorities discover any condition during the study that indicate that the study or study site should be terminated, this action may be taken after appropriate consultation between the Sponsor and the Investigator(s). The Sponsor has the right to terminate the participation of either an individual site or the complete study at any time. This action may be taken based on the recommendation of the independent DSMB.

Reasons for terminating may include, but are not limited to, the following:

- The incidence and severity of AEs in this or other studies indicates a potential health hazard to subjects;
- Subject enrolment is unsatisfactory;
- Data recording is inaccurate or incomplete to an unacceptable extent;
- Investigator(s) do not adhere to the protocol or applicable regulatory guidelines in conducting this study;

- Submission of knowingly false information from the study site to the Sponsor or regulatory authorities;
- Results of an interim analysis supporting terminating the study.

In the event that the study is terminated early, the Sponsor will provide specific guidance to investigational sites regarding the end-of-study procedures.

## 9. SAFETY REPORTING

### 9.1 Temporary halt for reasons of subject safety

In accordance to section 10, subsection 4, of the WMO, the sponsor will suspend the study if there is sufficient ground that continuation of the study will jeopardise subject health or safety. The sponsor will notify the accredited METC without undue delay of a temporary halt including the reason for such an action. The study will be suspended pending a further positive decision by the accredited METC. The investigator will take care that all subjects are kept informed.

### 9.2 AEs, SAEs, and SUSARs

#### 9.2.1 Adverse events (AEs)

Adverse events are defined as any undesirable experience occurring to a subject during the study, whether or not considered related to the IMP. Because the IMP has been marketed and used for over a hundred years and has a well-known safety profile, AEs will not be recorded unless they are serious (SAE or SUSAR).

#### 9.2.2 Serious adverse events (SAEs)

A serious adverse event is any untoward medical occurrence or effect that

- results in death;
- is life threatening (at the time of the event);
- requires hospitalisation or prolongation of existing inpatients' hospitalisation;
- results in persistent or significant disability or incapacity;
- is a congenital anomaly or birth defect; or
- any other important medical event that did not result in any of the outcomes listed above due to medical or surgical intervention but could have been based upon appropriate judgement by the investigator.

An elective hospital admission will not be considered as a serious adverse event.

All SAEs occurring between randomisation and day 7 have to be reported to the study Sponsor within 24 hours of Investigator's first awareness about the event, except for expected SAEs (see below). Any AE that occurs for the first time after day 7 is highly unlikely to be related to the IMPs. However, any SAE occurring between day 7 and the end of follow-up on day 90 ( $\pm$  14 days) for which a causal relationship between the IMP and the SAE is

considered at least a reasonable possibility should also be reported. This includes the reporting of SUSARs (see below).

The sponsor will report all unexpected SAEs through the web portal *ToetsingOnline* to the accredited METC that approved the protocol, within 7 days of first knowledge for SAEs that result in death or are life threatening followed by a period of maximum of 8 days to complete the initial preliminary report. All other unexpected SAEs will be reported within a period of maximum 15 days after the sponsor has first knowledge of the serious adverse events.

Expected SAEs are events that are known to occur in the conditions under study or with the IMP used in the trial as defined in its SmPC. As mentioned above, the IMP has been marketed and used for over a hundred years and has a well-known safety profile. Expected SAEs are defined in the protocol (Appendices 8 and 9). Expected SAEs are excluded from expedited reporting but should be documented in the eCRF within 7 days of the Investigator's first awareness about the event. Expected SAEs will be included as line listing in the annual safety report to the accredited METC.

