### **9.2.3 Suspected unexpected serious adverse reactions (SUSARs)**

Adverse reactions are all untoward and unintended responses to an investigational product related to any dose administered.

Unexpected adverse reactions are SUSARs if the following three conditions are met:

1. the event must be serious (see chapter 9.2.2);
2. there must be a certain degree of probability that the event is a harmful and an undesirable reaction to the medicinal product under investigation, regardless of the administered dose;
3. the adverse reaction must be unexpected, that is to say, the nature and severity of the adverse reaction are not in agreement with the product information as recorded in:
  - Summary of Product Characteristics (SmPC) for an authorised medicinal product.

All SUSARS occurring between randomisation and the end of follow-up at day 90 ( $\pm$  14 days) have to be reported by the local Investigator to the study Sponsor within 24 hours of Investigator's first awareness about the event. The sponsor will report the following SUSARs through the web portal *ToetsingOnline* to the METC in an expedited fashion:

- SUSARs that have arisen in the clinical trial that was assessed by the METC;
- SUSARs that have arisen in other clinical trials of the same sponsor and with the same medicinal product, and that could have consequences for the safety of the subjects involved in the clinical trial that was assessed by the METC.

The remaining SUSARs are recorded in an overview list (line listing) that will be submitted once every half year to the METC. This line listing provides an overview of all SUSARs from the study medicine, accompanied by a brief report highlighting the main points of concern. The expedited reporting of SUSARs through the web portal Eudravigilance or *ToetsingOnline* is sufficient as notification to the competent authority.

In the event this becomes applicable, the Sponsor will report all SUSARs to the competent authorities in other Member States in an expedited fashion, according to the requirements of the Member States.

The expedited reporting will occur not later than 15 days after the sponsor has first knowledge of the adverse reactions. For fatal or life threatening cases the term will be maximal 7 days for a preliminary report with another 8 days for completion of the report.

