The phase III randomised Rapid Intervention With Glyceryl Trinitrate in Hypertensive Stroke Trial-2 (RIGHT-2) was based on the promising findings in the studies above. RIGHT-2 randomised 1149 adults with presumed stroke within 4 h of onset who had a face-arm-speech-time score of 2 or 3 and systolic blood pressure of 120 mm Hg or higher to transdermal GTN (5 mg once daily for 4 days) or a similar sham dressing. Treatment was started in the ambulance by paramedics, with treatment continued in hospital. The median time to randomisation was 71 min (IQR, 45 to 116). 597 (52%) patients had ischaemic stroke, 145 (13%) had intracerebral haemorrhage, 109 (9%) had transient ischaemic attack, and 297 (26%) had a non-stroke mimic at the final diagnosis of the index event. In the GTN group, participants' systolic blood pressure was lowered by 5.8 mm Hg compared with the sham group ( $p<0.0001$ ), and diastolic blood pressure was lowered by 2.6 mm Hg ( $p=0.0026$ ) at hospital admission. Early administration of GTN did not have an effect of functional outcome in patients with a final diagnosis of stroke or transient ischaemic stroke (adjusted common odds ratio for poor outcome (acOR), 1.25; 95% CI, 0.97 to 1.60;  $p=0.083$ ), nor in the complete population (acOR, 1.04; 95% CI, 0.84 to 1.29;  $p=0.69$ ). There was also no difference in the risk of death at 90 days (19% vs 17%; acOR, 1.11; 95% CI, 0.84 to 1.47;  $p=0.47$ ) or in the risk of serious adverse events. Remarkably, GTN was associated with an

improved functional outcome in patients with a stroke mimic (acOR, 0.54; 95% CI, 0.34 to 0.85; p=0.0081). This positive finding was not localised to any particular type of mimic. The observed tendency towards harm of GTN in RIGHT-2 was particularly seen in patients with intracerebral haemorrhage, very early stroke (<1 h), and severe stroke [Figure 3]. Furthermore, patients with intracerebral haemorrhage treated with GTN had larger haematoma size and more mass effect on hospital admission.

**Figure 3:** Effect of GTN versus sham on mRS score at day 90 in patients with a final diagnosis of stroke or TIA.

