### **Central nervous system**

Brain oedema

Cerebral herniation

Cerebellar herniation

Delirium

Depression

Epileptic seizure

Haemorrhagic transformation of the infarct

Headache

Haematoma expansion

Hydrocephalus

Intraventricular extension of haemorrhage

Increased intracranial pressure

Progressive stroke / Stroke in evolution

Recurrent ischaemic stroke

Recurrent intracerebral haemorrhage

Recurrent stroke

Retinal ischaemia

Sleep disorder

Status epilepticus

Transient ischaemic attack

Transient monocular blindness

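### Sections 9.2.2 and 9.2.3 give conflicting reporting rules for a serious event that is listed in Appendix 9 and suspected to be caused by GTN

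*Protocol*

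**What the plan says.** Protocol section 9.2.2 requires SAEs between randomisation and day 7 to be reported to the sponsor "within 24 hours of Investigator's first awareness about the event, except for expected SAEs (see below"). It describes the exempt class in two alternatives: "Expected SAEs are events that are known to occur in the conditions under study or with the IMP used in the trial". The reference lists are named next: "Expected SAEs are defined in the protocol (Appendices 8 and 9"). Appendix 8 gives the known side effects of GTN and Appendix 9 the common serious complications of stroke. The consequence is: "Expected SAEs are excluded from expedited reporting but should be documented in the eCRF within 7 days of the Investigator's first awareness about the event". These events then go to the METC as a line listing in the annual safety report.

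Section 9.2.3 uses a different test. An adverse reaction is unexpected if "the nature and severity of the adverse reaction are not in agreement with the product information as recorded in" the SmPC. SUSARs from randomisation to the end of follow-up must reach the sponsor within 24 hours. The sponsor then has at most 15 days. For fatal or life-threatening cases it has 7 days for a preliminary report and another 8 to complete it.

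The central nervous system list in Appendix 9 includes "Haematoma expansion". Section 13.1 e says of RIGHT-2 that "patients with intracerebral haemorrhage treated with GTN had larger haematoma size and more mass effect on hospital admission".

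**The concern.** Whether an event is common in the disease and whether a suspected drug reaction is already known from the product information are separate questions. Section 9.2.2 merges them. An event becomes expected because stroke can cause it, even when the investigator thinks that GTN caused it in this patient. Section 9.2.3 keeps them apart.

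The overlap is more than formal. The trial is open-label, so an investigator can form a suspicion about the patch. Treatment starts before imaging, so patients with intracerebral haemorrhage will receive it. Sections 1.10 and 13.2 both say that the RIGHT-2 subgroup findings call for close safety monitoring. A suspected GTN-related haematoma expansion could be filed as an expected complication and not be assessed as a possible SUSAR. The sponsor and the METC would then learn of it by the slower route.

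**Working it through.** No sample size, power or event count is involved, so the check sets the rules side by side for one case: a serious haematoma expansion before day 7 in a patient on GTN, which the investigator suspects is due to GTN.

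| Step | Section 9.2.2 with Appendices 8 and 9 | Section 9.2.3 |
|---|---|---|
| Reference for expectedness | Disease or drug; Appendix 9 or Appendix 8 | SmPC only, by nature and severity |
| Is the event in the reference? | Yes, Appendix 9 | Not in Appendix 8; SmPC not shown |
| Does suspected cause matter? | No condition stated | Yes, it is one of the three SUSAR conditions |
| Classification | Expected SAE | SUSAR, if the SmPC does not list the event |
| Site to sponsor | eCRF entry within 7 days | 24 hours |
| Sponsor to METC | Line listing, once a year | 15 days; if fatal or life-threatening, 7 days plus 8 to complete |

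**Difference in time.** Site to sponsor: 7 days − 1 day = up to 6 days later. Sponsor to METC: a yearly listing instead of 7 or 15 days.

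**Which events are affected.** Appendix 9 also lists haemorrhagic transformation, intraventricular extension, increased intracranial pressure, and cerebral and cerebellar herniation. Appendix 8 lists none of these. The conflict therefore exists in principle for each of them when GTN is suspected. Raised intracranial pressure does appear in section 6.1, but as a contraindication, not as a side effect.

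**Which events RIGHT-2 supports, as the protocol describes it.**
- Larger haematomas and more mass effect were observed (sections 1.8 and 13.1 e).
- Early haematoma expansion is offered as a mechanism.
- Raised intracranial pressure is a hypothesis from an animal study, and the protocol sets other studies against it.
- Herniation and haemorrhagic transformation are not named.

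**Order in time.** For SAEs after day 7, section 9.2.2 requires a report whenever a causal relation to GTN is a reasonable possibility, and that sentence makes no exception for listed events. Up to day 7, which includes the 24 hours of treatment, a listed event is exempt from the 24-hour report whatever its cause. Yet the same section calls a relation to treatment very unlikely for events that first occur after day 7. The rule is loosest when causation is most plausible.

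**Precedence.** Neither section refers to the other in a way that settles the overlap, and no sentence says which governs.

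**The case against.** **A site can satisfy both sections.** Section 9.2.2 lifts a 24-hour duty but does not forbid a 24-hour report. A site that reports within 24 hours and completes the eCRF has complied with both. This stands. The literal clash is at sponsor level, where one section excludes the event from expedited reporting and the other requires it. For the site, the problem is that 9.2.2 read alone tells it that no such report is needed.

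**Section 9.2.3 is the specific rule for suspected reactions and would naturally prevail.** This is a fair reading, and section 9.3 assumes that SUSARs are reported in an expedited way. So the protocol does not prescribe that these events go uncounted as SUSARs. But the reader has to infer the precedence, and the wording of 9.2.2 is unconditional.

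**Safety monitoring is provided.** A reader might infer that the promised close monitoring is missing. The documents do not support that. Section 13.2 assigns it to the DSMB. Section 9.5 provides unblinded safety analyses after every 100 patients complete follow-up, until at least patient 1000, with listings of all SAE reports. Symptomatic intracerebral haemorrhage is a recorded safety parameter (8.1.3), and SAEs in the first 7 days are a secondary outcome (8.1.2). For a complication that is common without treatment, comparing the arms is the better detector of excess harm. It does not settle how a single suspected reaction is to be reported.

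**Not every listed event is a harm flagged in RIGHT-2.** This stands; only haematoma size and mass effect were observed. Arterial hypotension, also in Appendix 9, adds nothing, because Appendix 8 lists hypotension as a drug effect.

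**The number of haemorrhage patients does not measure the defect.** RIGHT-2's share of all randomised patients gives 145/1149 × 1400 = 177. Its share among stroke and TIA patients, with this protocol's 10% mimics, gives 145/(597 + 145 + 109) × 1260 = 215. These are patients at risk under borrowed shares. They are not haematoma expansions, suspected reactions or misrouted reports.

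**Conclusion.** The contradiction is real and should be corrected. For a serious event that is listed in Appendix 9 and suspected to be caused by GTN, section 9.2.2 gives up to 7 days to the eCRF and a yearly listing. Section 9.2.3 gives 24 hours to the sponsor and 7 or 15 days to the METC. The documents give no basis for estimating how many reports would be affected.

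The conclusion that such an event is a SUSAR assumes that the SmPC, like Appendix 8, does not list it as an adverse reaction. The SmPC is not shown, and section 6.1 notes that several exist with small differences. The difference in references for expectedness, and the missing causality condition in 9.2.2, do not depend on that assumption.

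The defect is limited to the route, speed and classification of individual suspected reactions. Capture in the eCRF and review by the DSMB are unaffected.

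**What to change.** Amend section 9.2.2 so that the Appendix 9 exemption applies only to SAEs for which a causal relation to GTN is not considered a reasonable possibility. State that any SAE for which such a relation is a reasonable possibility, from randomisation onward, is assessed for expectedness against the SmPC only and reported under section 9.2.3. This also removes the anomaly around day 7.

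Sending haematoma expansion and related events by the 24-hour route whatever their cause would be a further choice. The contradiction does not require it.

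The cost is an amendment to the text and a few additional 24-hour reports. No new assessments or data fields for outcomes are needed.
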